## 1. Study Protocol

Potential participants were Veterans with recurrent binge eating seeking weight loss were recruited from VA's Weight Management Program, MOVE! at two VA sites: West Haven, CT and Northampton, MA between January 2018 and May 2022. As recruitment for this study was underway during the COVID-19 pandemic, Veterans were first recruited from in-person MOVE! orientation sessions between January 2018 and March 2020 and then additionally from VA's remote TeleMOVE! program starting in July 2020. Eligibility required age 21+, Body Mass Index (BMI) $\geq$ 25, and DSM-5 clinical/subclinical BED. Exclusions were: attendance of more than 4 MOVE! group sessions in the prior year, active psychosis or suicidal ideation, medical or psychiatric illness or cognitive deficits that interfere with providing consent or completing assessments, and pregnancy or lactation. The study received IRB approval by the VA Connecticut Healthcare System, which provides oversight for both West Haven, CT, and Northampton, MA facilities.

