### *1.6 Randomization*

Stratified randomization (clinical BED (n=101) and subclinical BED (n=8)) to the two conditions was performed with a computer-generated sequence.

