### *1.7 Treatment Conditions*

#### MOVE! (Treatment-as-Usual)

All participants received VA's Weight Management Program, MOVE!, as administered at their site, without research staff involvement. MOVE! is an evidence-based behavioral weight management program that includes treatment procedures, clinical algorithms, patient and provider information, and instructional materials. The program was widely disseminated and implemented beginning in January 2006 [17]. The 60-minute groups cycle every 16 weeks and are led by trained and monitored MOVE! clinicians who are from the following disciplines: primary care, psychology, nutrition, and physical therapy. Clinicians utilize materials available in hard copy or on-line, and encourage the use of, but do not require or provide, food diaries. Due to the COVID-19 pandemic, MOVE! modalities offered for the present study were expanded to include VA's virtual MOVE! and TeleMOVE! programs. Virtual MOVE! involves synchronous delivery of MOVE! groups via VA Video Connect (i.e., telehealth). TeleMOVE! involves asynchronous delivery of MOVE! content via home-based technology and as needed clinician phone contact. Thus, MOVE! in the present study involved two cohorts: 1) **in-person** MOVE! (n=40), and 2) **virtual** MOVE! or TeleMOVE! (n=69).

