#### Brief, Clinician-led Cognitive-Behavioral Therapy for BED

One-half of participants received CBT in addition to MOVE!. The CBT was administered via 9 hourly individual sessions over a three-month treatment period. The treatment was led by a licensed clinical psychologist or social worker following a CBT for BED manual specifically developed for this project. Based upon a manual from previous studies [18, 19], the manual was adapted for the VA healthcare user population using iterative input from VA clinicians experienced with Veteran and eating disorder care, a Veteran Engagement Group paid to provide investigators with feedback about the design of Veteran research, and a Veteran who served as one of the study clinicians for this project. The most notable adaptions included person-first language, Veteran-centered examples, graphical representation of concepts, and writing at the seventh-grade reading level. Four clinicians received training from the Principal Investigator (PI; RM), feedback on videorecording of every session for clinicians' first two cases, feedback and adherence ratings of 10% of sessions thereafter, and weekly supervision from the PI (RM). Participants completed daily records of food intake and binge episodes, and these were reviewed and checked weekly by clinicians. The treatment consisted of three overlapping phases. The first phase involved building a collaborative therapeutic relationship, educating the patient about the diagnosis of BED and maintaining factors of binge eating, and utilizing

behavioral strategies (self-monitoring and goal setting and problem-solving to achieve structured patterning, timing and settings for eating). The second phase integrated cognitive skills such that patients learned to identify and challenge maladaptive thoughts and emotional triggers related to eating/restriction and weight/shape. The final phase focused on the maintenance of change and relapse prevention. Brief clinician-led CBT was conducted in-person before the onset of the COVID-19 pandemic and by phone after.

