## 2. Statistical Analysis Plan

Baseline characteristics were compared between the treatment groups using ANOVA and chi-squares as appropriate in order to determine the level of success of the randomization. Distributions of outcomes were examined to determine if assumptions of specific model types were met. Change of model type as well as transformation of the data were considered if model assumptions were not met. Mixed-effects models, a method for statistical modeling that uses both fixed effects and random effects, were used to examine continuous outcomes such as eating pathology binge eating frequency, mental health symptoms, and percent weight loss for completer, as well as intent-to-treat (all randomized persons), analyses. Logistic regression models were used for categorical outcomes such as binge remission and achieving clinically meaningful weight loss (i.e., 5% weight loss or greater). The outcomes were transformed to approach normality as needed and models controlled for treatment, time, gender, age, and baseline BMI.

*2.1 Cohort (in-person vs remote) analyses.* There were 40 (37%) subjects in cohort 1 and 69 (63%) in cohort 2. All the analyses with cohort (categorical variable) added to the models were run and conclusions were substantively the same.

*2.2 Missing Data.* Missing data was minimized by having participants complete with assistance of research assistants. The mixed-effects models addressed missing data for continuous outcomes as the modeling makes use of all available data for each participant, even when there are different numbers of observations. [79]

*2.3 Missingness analyses.* We focused on the missingness of the primary outcome averages binge per month (over past 3 months). Outcome was missing for 11.9% of subjects at month 3, 19.3% at month 9, and 24.8% at month 15. Overall, these 3 timepoints, 35.8% of subjects had incomplete outcome data (missing outcome at any of timepoints). There was no evidence of a difference between groups in missingness at any timepoint or overall (all p-values $\geq$ .10).

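### Site enters no described model or sensitivity analysis, although two sites each ran their own MOVE! programme; adding it would bring a modest gain in precision and protection against chance imbalance

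*Combined protocol and SAP*

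**What the plan says.** Section 1 says that recruitment took place "at two VA sites: West Haven, CT and Northampton, MA". Section 1.7 says that all participants received MOVE! "as administered at their site, without research staff involvement", and that "One-half of participants received CBT in addition to MOVE". MOVE! is therefore the control treatment and also the background treatment in the experimental arm.

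Section 1.6 gives the allocation method: "Stratified randomization (clinical BED (n=101) and subclinical BED (n=8)) to the two conditions was performed with a computer-generated sequence". It mentions neither site nor blocking.

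Section 2 states that the "models controlled for treatment, time, gender, age, and baseline BMI". Two sets of additional models follow. Section 2.1 adds cohort: "All the analyses with cohort (categorical variable) added to the models were run and conclusions were substantively the same". Section 2.4 adds three baseline variables associated with missingness: highest weight, weight-related quality of life and food addiction. Neither set adds site. The number of participants per site is not given, overall or by arm.

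**The concern.** Site is a known feature of the design, fixed before randomisation. Because research staff had no part in delivering MOVE!, any local differences in how it was run, or in who attended, were left as they were. If those differences relate to outcome, two things follow from leaving site out:

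- Between-site variation stays in the residual, so the standard error is a little larger than it need be.
- If the arms happened to differ in site mix, part of the site difference sits in the one estimate the trial produced, and a reader cannot see how much.

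Neither is a bias of the method. At stake are a small amount of precision and the ability to answer an obvious question about a two-site trial with numbers.

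**Working it through.** **Inputs from the documents.** The cohort counts are "There were 40 (37%) subjects in cohort 1 and 69 (63%) in cohort 2". They sum to 40 + 69 = 109, which matches the strata, 101 + 8 = 109. The percentages reproduce: 40/109 = 36.7% and 69/109 = 63.3%. The documents state no sample-size calculation, effect size or site count against which the rest could be checked.

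**Assumptions.** Arms of 54 and 55 (the text says one-half); allocation unrestricted with respect to site; the smaller site holding 20% to 50% of participants; a site difference of d = 0.3 to 0.5 outcome SD; a single continuous outcome with complete data. None of these is given in the documents.

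**1. Chance imbalance in site share between arms.** SD = √[p(1 − p)(1/54 + 1/55)].
- p = 0.5: √(0.25 × 0.0367) = 0.096
- p = 0.7: √(0.21 × 0.0367) = 0.088

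The exact hypergeometric calculation gives 9.6 points for an even split and 7.7 points if the smaller site holds 20%. The chance of a difference of 20 points or more is 3.5% and 0.8% respectively.

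**2. Effect on the realised estimate, even split.** Shift = imbalance × d. The unadjusted standard error is √(4/109) = 0.192 SD.

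| Imbalance | Shift at d = 0.3 | Shift at d = 0.5 | As share of standard error |
|---|---|---|---|
| 1 SD (0.096) | 0.029 | 0.048 | 0.15 to 0.25 |
| 1.96 SD (0.188) | 0.056 | 0.094 | 0.3 to 0.5 |

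The second row is exceeded in only about 5% of allocations.

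**3. Precision.** Share of variance explained by site = p(1 − p)d². The standard error is multiplied by √(1 − share).

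| Split | d = 0.3 | d = 0.5 |
|---|---|---|
| 50/50 | 0.0225, SE falls 1.1% | 0.0625, SE falls 3.2% |
| 70/30 | 0.0189, SE falls 0.9% | 0.0525, SE falls 2.7% |
| 80/20 | 0.0144, SE falls 0.7% | 0.0400, SE falls 2.0% |

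Spending one degree of freedom returns about half a percentage point: √(103/102) = 1.005, taking roughly 103 residual degrees of freedom.

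**4. Limits of this arithmetic.** It is for a single measurement in a linear model. The plan has assessments at baseline and at 3, 9 and 15 months, and does not say whether the baseline value is one of the modelled outcomes. If it is, a stable site difference largely cancels from the treatment-by-time contrast. Only a site difference in change would then matter, and a site main effect alone would not capture it. The variance formula also does not carry over to the logistic models.

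**The case against.** The strongest objection is that little is at stake. Chance imbalance under randomisation is already part of the sampling error that the unadjusted standard error reflects. The site effect of 0.3 to 0.5 SD is assumed, and section 1.7 describes MOVE! as one programme with common materials and trained, monitored clinicians. The larger shifts need an unusual allocation. In the logistic models, an added covariate changes the odds ratio being estimated and draws on limited events: with the primary outcome missing for 24.8% at month 15, about 109 × 0.752 = 82 participants contribute. All of this stands, and it is why the point is a minor one.

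It is also fair to say that the random effects are not specified, so a site random effect cannot be strictly ruled out. None is mentioned, however, and the logistic models are described without random effects.

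A reader might make the same complaint about cohort and ask for it in the main model. The documents do not support that. Section 2.1 reports that every analysis was re-run with cohort added and that the conclusions held. The cohorts arose from the pandemic during recruitment, so cohort could not have been a stratification factor from the outset. Promoting it now would be a change to the main model made with results in hand. What remains is only that section 2.1 gives no estimates.

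**Conclusion.** The gap for site is real: two sites, locally run MOVE!, no described site stratification, and no described model or sensitivity analysis that includes site. Its size is modest. With an even split and a site difference of 0.3 to 0.5 SD, adjustment would take about 1% to 3% off the standard error before the small cost in degrees of freedom, and less with an uneven split or a smaller site difference. A realised shift as large as 0.06 to 0.09 SD needs both that site difference and a 1.96-SD imbalance.

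A reader might infer that the CBT estimate is confounded by site or that the trial's conclusions are in doubt. Neither follows. The estimator is unbiased under randomisation, and the documents contain no arm-by-site counts or site effects from which an actual imbalance could be shown.

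**What to change.** - Add site (two levels) as a fixed effect in the mixed models. If baseline is modelled as an outcome, add site-by-time as well, and state which approach was used.
- Add site to the logistic models for binge remission and 5% weight loss where event counts allow.
- Because the text already reports results, show the site-adjusted estimates with intervals beside the reported ones, and label them as added later.
- Report the number of participants by arm and site.
- Leave cohort as a sensitivity analysis, and show the cohort-adjusted estimates and intervals that section 2.1 only summarises.

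The cost is a re-run with a variable known from recruitment. Site uses one degree of freedom; site-by-time uses one more if time is linear, or three if the four assessments are treated as categories. In the logistic models the conditional odds ratio will differ slightly from the reported one even without any imbalance, and the report should say so.
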